### **8.1.6 Re-treatment for Progression during Follow-up**

Subjects who stop IMP without disease progression and who experience disease progression within 12 months of their last dose of IMP may receive additional IMP for up to 48 weeks provided that they meet the criteria in Sections 8.1.2, 8.1.3 and 8.1.4 and have not received other systemic therapy for their cancer. Biopsy of a progressing lesion should be obtained, if feasible. The Medical Monitor must be consulted before a subject in follow-up begins re-treatment. Subject must be re-consented prior to restarting IMP. (Upon implementation of Amendment 3, subjects who discontinued IMP without disease progression will not be allowed to receive additional IMP upon disease progression.)

The schedule of assessments for Cycle  $\geq 3$  should be followed, except that PK, PD, and anti-drug antibody (ADA) assessments are not required.

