1 INTRODUCTION

This Statistical Analysis Plan (SAP) has been developed after review of Kyowa Kirin Pharmaceutical Development, Inc. Protocol 0761-014 (Amendment 2, dated 05 Dec 2016), along with the corresponding electronic case report forms (eCRF). This SAP describes the analysis sets and specific details for the statistical methods to be used for the analysis and reporting of all efficacy, safety, pharmacokinetic parameters, and immunogenicity data collected during the conduct of Protocol 0761-014. This SAP supersedes the statistical considerations identified in Protocol 0761-014 with regards to details of the analyses; where considerations are substantially different, they will be identified as such in this document. In the event that the protocol has amendment(s) that do not have an impact on the statistical analysis methodology, this SAP will not require an amendment. This SAP has been developed and finalized prior to database lock of the clinical database for Protocol 0761-014. If additional analyses are required to supplement the planned analyses described in this SAP, they may be performed and will be identified in the Clinical Study Report (CSR).

This SAP is being written with consideration of the recommendations outlined in the International Conference on Harmonization (ICH) E9 Guideline entitled “Guidance for Industry: Statistical Principles for Clinical Trials” and the most recent ICH E3 Guideline, entitled “Guidance for Industry: Structure and Content of Clinical Study Reports.”

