4.8 Study Drug Exposure and Compliance

The maximum number of cycles initiated, cycles that a subject initiated, extent of exposure (defined as Last Dose Date – First Dose Date + 1), and the number of infusions administered (mogamulizumab: Days 1, 8, 15, 22 of the first cycle and Days 1 and 15 of each subsequent cycle; nivolumab: Days 1 and 15 of each cycle) per subject will be summarized for each medication. Infusion time (in minutes) per administration (overall, at 1st – 4th infusion, and later for mogamulizumab; at 1st and 2nd infusions, and later for nivolumab) will also be presented. These parameters will be summarized for the Safety Analysis Set.

Cumulative dose statistics will be calculated for mogamulizumab as follows.

- Cumulative actual dose (mg/kg): Sum of {Actual dose administered (mg)/Body weight (kg)};
- Cumulative assigned dose (mg/kg): Sum of {Planned dose (mg/kg)};
- Relative dose intensity (%):

$$\frac{\text{Number of doses administered in Cycle 1} + \text{Number of doses administered in Subsequent Cycles} \times 2}{[(\text{Number of cycles initiated}) \times 4]} \times \frac{\text{Number of cycle initiated} \times 28}{\text{Last dose date} + n^* - \text{First dose date}} \times 100$$

where $n^* = 7$ when the patient was only treated for 1 cycle, otherwise, $n^* = 14$.

Note that body weight for each infusion is defined as weight entered at the visit for calculation of the dose level.

Similarly, cumulative actual dose (mg), cumulative assigned dose (mg), and relative dose intensity (%) will be calculated for nivolumab as well. Note that the assigned dose for nivolumab is 240 mg per administration.

- Cumulative actual dose (mg): Sum of {Actual dose administered (mg)};
- Cumulative assigned dose (mg): Sum of {Planned dose (mg)} = (Last nivolumab dose date – First nivolumab dose date) × 240/14;
- Relative dose intensity (%): Cumulative actual dose/Cumulative assigned dose × 100.

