4.13.1 Adverse Events

All subjects will be assessed regularly for the potential occurrence of adverse events (AEs) from the date of informed consent to 100 days after the last dose of IMP. The incidence of treatment-emergent AEs (TEAEs) will be summarized and tabulated using MedDRA (version 18.1), by System Organ Class (SOC) and Preferred Term (PT). A TEAE is defined as an AE that first occurs or worsens in severity on or after the first dose of any IMP and within 100 days after the last dose of IMP.

The National Cancer Institute Common Terminology Criteria for Adverse Events (CTCAE) (Version 4.03) will be used to grade both clinical and laboratory AEs. A subject with several occurrences of the same AE will be counted once and classified by the most severe occurrence. AEs with missing severity ratings will be classified as having unknown severity, but will be assigned Grade 3 severity for analysis and summarization.

The relationship of each AE to the IMP will be classified as related or unrelated. Any AE with an eCRF description of related will be considered related. A subject with several occurrences of the same AE will be counted once and classified as related if at least one of them is classified as related. An AE with a missing relationship to IMP will be assumed to be related to IMP for the purpose of analysis and summarization. Relationship of AEs to mogamulizumab and nivolumab will be separately recorded and analyzed.

An overview of adverse events for the Safety Analysis Set will be provided, summarizing the incidence of the following:

- Any TEAEs; Mogamulizumab-related TEAEs; Nivolumab-related TEAEs;
- Any NCI/CTCAE Grade 3/4/5 TEAEs; Mogamulizumab-related NCI/CTCAE Grade 3/4/5 TEAEs; Nivolumab-related NCI/CTCAE Grade 3/4/5 TEAEs;
- Any Treatment-emergent SAEs; Mogamulizumab-related treatment-emergent SAEs; Nivolumab-related treatment-emergent SAEs;
- Any discontinuation of study drug due to TEAEs; discontinuation of Mogamulizumab due to Mogamulizumab-related TEAEs; discontinuation of Nivolumab due to Nivolumab-related TEAEs;
- Any NCI/CTCAE Grade 5 TEAEs; Mogamulizumab-related NCI/CTCAE Grade 5 TEAEs; Nivolumab-related NCI/CTCAE Grade 5 TEAEs;

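### For any subject re-treated before Amendment 3, the SAP counts the off-drug gap as exposure and under-dosing, and its PFS rule can overwrite the progression that triggered re-treatment

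*SAP*

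**What the plan says.** - **Who could be re-treated.** Protocol 8.1.6: "Subjects who stop IMP without disease progression and who experience disease progression within 12 months of their last dose of IMP" were eligible. They "may receive additional IMP for up to 48 weeks provided that they meet the criteria" of Sections 8.1.2 to 8.1.4 and had received no other systemic cancer therapy. Medical Monitor consultation and re-consent were also required.
- **Withdrawal.** The same section adds that, upon implementation of Amendment 3, "subjects who discontinued IMP without disease progression will not be allowed to receive additional IMP upon disease progression". Protocol 6.3 and the synopsis say the same.
- **SAP basis.** SAP 1 says it was developed after review of the protocol at "Amendment 2, dated 05 Dec 2016". The SAP text contains no rule for re-treatment.
- **Exposure and dose intensity.** SAP 4.8 gives "extent of exposure (defined as Last Dose Date – First Dose Date + 1". The time denominator for mogamulizumab RDI is last dose date plus n* minus first dose date, where n* is 7 for a single cycle and 14 otherwise. The nivolumab assigned dose is the days from first to last nivolumab dose, times 240/14.
- **TEAEs.** SAP 4.13.1 counts events that begin or worsen "on or after the first dose of any IMP and within 100 days after the last dose of IMP". Protocol 10.3.2.1 collects all AEs to 100 days after the last dose and, after that, only SAEs believed related to study drug or a protocol procedure.
- **Response and PFS.** Under SAP 4, the primary BOR window ends at subsequent anti-cancer therapy, and a sensitivity BOR also ends at first radiographic progression. For subjects with a BOR of CR or PR, the PFS event is the first progression or death after the last documented CR or PR.

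**The concern.** A subject re-treated before Amendment 3 stays in the database after the option was withdrawn. For that subject the last dose is the last dose of the second course, so every quantity running from first to last dose takes in a period when no drug was scheduled. Full compliance on both courses would be reported as a longer exposure at a reduced intensity.

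The efficacy rules meet the same case differently. Re-treatment is study drug, and it was open only to subjects who had received no other systemic cancer therapy. On a natural reading it is therefore not subsequent anti-cancer therapy and does not close the primary BOR window. A response on the second course could become the subject's BOR and TTR. It would also move the PFS event past the progression that led to re-treatment.

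**Working it through.** The documents give no figure to reproduce here. The check applies the SAP 4.8 formulas first to one compliant course and then to two compliant courses separated by a gap.

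**One compliant course.** Mogamulizumab RDI is 100.0% for 1, 2, 6 and 24 cycles. Nivolumab RDI is 200%, 133%, 109% and 102%, because its denominator leaves out the interval after the last dose. That is a separate matter, but it means the nivolumab comparator below is the formula applied by course, not 100%.

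**Worked case (assumed, not taken from the documents).** First course of 12 cycles, restart 26 weeks (182 days) after the last dose, second course of 6 cycles, with every dose on schedule. Re-treatment is taken as Days 1 and 15 of each cycle.

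- First course: 24 nivolumab doses; the last is on Day 1 + 14 × 23 = 323.
- Restart: Day 323 + 182 = 505. Twelve doses; the last is on Day 505 + 14 × 11 = 659.
- Exposure under the SAP: 659 − 1 + 1 = 659 days. By course: 323 + 155 = 478 days. The excess is 181 days, and 659/478 = 1.38 (+38%).
- Nivolumab RDI under the SAP: (36 × 240)/(658 × 240/14) = 504/658 = 76.6%. By course: 504/(322 + 154) = 105.9%.
- Mogamulizumab doses: 4 in Cycle 1 and 34 afterwards. RDI under the SAP: [(4 + 34 × 2)/(18 × 4)] × [18 × 28/(659 + 14 − 1)] = (72/72) × (504/672) = 75.0%. Each course alone gives 100%. In Tables 14.1.3.1.1 and 14.1.3.1.2 the subject moves from the 90–110% band to the 70–90% band.
- TEAE window: 100 days after Day 323 is Day 423. Days 424 to 504 (81 days) fall inside the SAP window but outside general AE collection.

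**Range.** Course lengths and gaps are assumptions. Gap is last dose to restart; the excess exposure is always gap − 1 days.

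| First course / gap / second course | Exposure, SAP vs by course (days) | Mogamulizumab RDI | Nivolumab RDI | Gap days beyond 100 |
|---|---|---|---|---|
| 24 cycles / 101 d / 12 cycles | 1082 vs 982 (+10%) | 92.1% | 93.2% | 0 |
| 24 / 365 d / 12 | 1346 vs 982 (+37%) | 74.2% | 74.9% | 264 |
| 6 / 365 d / 12 | 842 vs 478 (+76%) | 58.9% | 59.9% | 264 |
| 3 / 365 d / 3 | 506 vs 142 (+256%) | 32.4% | 33.3% | 264 |

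**Response.** One second-course responder adds 1/36 = 2.8 points to the ORR of the largest cohort and 1/17 = 5.9 points to that of the smallest (SAP Table 1). With N = 32, going from 2 to 3 responders moves the estimate from 6.2% (exact 95% CI 0.8–20.8) to 9.4% (2.0–25.0).

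**PFS.** In the worked case the triggering progression precedes Day 505. A second-course CR or PR comes after Day 505 and needs confirmation at least 4 weeks later, so the last CR or PR falls after Day 505 + 28 = 533. The PFS event or censoring date is later still, and the triggering progression is no longer the event. Table 14.2.4.1 carries one PFS analysis and no sensitivity version.

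**The case against.** The strongest reply is that the affected group may be empty. Re-treatment needed a stop without progression, progression within 12 months, no other systemic therapy, the dosing and discontinuation criteria met, re-consent, and consultation with the Medical Monitor. It is now barred. A SAP table shell also cites Amendment 4, so the SAP was not wholly frozen at Amendment 2. All of this is fair, and it limits the size of the point. It does not supply a rule for anyone re-treated earlier.

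On exposure, infusion counts are summarised and Listings 16.2.5.1 to 16.2.5.3 give dose dates, so a careful reader could recover the gap. The summary tables and RDI bands would still carry the distorted values.

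On response, much of the reply stands. Protocol 8.1.5 explains why early radiographic progression may not mean lack of response, and the TTR and DOR table footnotes say the primary method disregards progression. Counting post-progression responses is deliberate. The sensitivity BOR, TTR and DOR stop at first radiographic progression, so they leave out second-course responses whenever the triggering progression was radiographic. They cannot, however, separate those responses from responses during continued first-course treatment beyond progression.

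On TEAEs, few events can be misclassified, because beyond 100 days only related SAEs are collected unless collection restarts with re-treatment.

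**Conclusion.** The concern holds, as a minor one. For a re-treated subject, the stated exposure and RDI formulas give wrong values: in the worked case 659 days instead of 478, with RDIs of 76.6% and 75.0% for full dosing. Over the assumed range the excess exposure is 10% to 256%. The PFS rule would displace the triggering progression if the subject responds again, and no planned analysis shows the alternative. The BOR and TTR effect is bracketed; the TEAE effect is small.

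Three stronger readings are not supported:

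- A reader might infer that the response windows also run from first to last dose. They do not: primary BOR ends at subsequent anti-cancer therapy.
- A reader might infer that counting responses after progression is itself an error. It is the plan's stated choice. What is missing is a decision on responses obtained with a second course.
- A reader might infer that reported results are distorted. The number re-treated is not given and may be zero.

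The conclusion rests on reading re-treatment as study drug rather than subsequent anti-cancer therapy. The sizes rest on the assumed courses and gaps.

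**What to change.** Add a course flag to the dosing data and the following wording to the SAP:

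- Compute extent of exposure and both RDIs per course, or sum on-treatment days across courses.
- Define a TEAE as onset or worsening during either course or within 100 days after the last dose of that course. Keep re-treatment TEAEs in the summary tables, flagged by course. Safety is the primary endpoint, so moving them to listings would remove on-drug toxicity from the main tables. Later gap events remain in Listing 16.2.7.1, which already marks non-treatment-emergent events.
- For a re-treated subject, fix the PFS event at the progression that triggered re-treatment.
- Do not count second-course responses towards first-course BOR, TTR or DOR; list them separately. Leave the existing handling of responses during first-course treatment beyond progression unchanged.
- Report in the CSR how many subjects were re-treated before Amendment 3.

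The cost is one derived variable and a few sentences. TEAE and responder counts may fall slightly, and PFS for a re-treated responder would shorten. If nobody was re-treated, one sentence in the CSR settles the matter.

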**7.5 Removal of Subjects from Therapy or Assessment**

A subject is free to withdraw his/her consent and discontinue study treatment or participation in the study at any time for any reason. A subject may also be discontinued from the treatment, at the discretion of the Investigator and/or sponsor, for any of the following reasons:

- Withdrawal of consent from further treatment with IMP;

- Withdrawal of consent from the study;
- AEs (see Section 10.3);
- Required use of prohibited concomitant medications;
- Non-compliance that, in the opinion of the Investigator or Sponsor, warrants withdrawal (e.g., refusal to adhere to scheduled visits);
- Major protocol violation;
- It is not considered in the best interest of the subject to continue;
- Pregnancy;
- Subjects who have unequivocal documented disease progression or symptomatic disease progression and are not eligible for continued treatment (see Section 8.1.5);
- Lost to follow-up;
- Administrative reasons (e.g., termination of the study).

The Investigator must maintain a record of all subjects who discontinue from the study prior to completion; the reason(s) for study discontinuation will be documented. In the event that a subject chooses to withdraw from the study, the Investigator should make a reasonable attempt to obtain and record the reason(s) for withdrawal, if possible, although the subject is not obligated to provide such a reason.

If treatment is discontinued, **both IMPs will be discontinued** (e.g., subjects will not be allowed to continue one investigational agent if the other is discontinued). For any case of treatment discontinuation (whether or not the subject is at the clinical site), the Investigator should ask the subject to complete the End-of-Treatment (EOT) and Follow-up visit procedures, provided that the subject has not withdrawn consent for those procedures (see Table 9-1 and Table 9-2 for the Schedule of Assessments). Subjects withdrawn from study without unequivocal disease progression or withdrawal of consent for follow up should continue tumor assessments until a new anticancer therapy is started, unequivocal disease progression is documented, withdrawal of consent for the follow-up contacts, or death.

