### **8.1.2 Dose Reduction and Dose Delay**

Doses of IMPs may be interrupted, delayed, or discontinued depending on how well the subject tolerates the treatment.

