#### **8.1.2.1 Dose Reduction**

There will be no intra-patient dose reduction of either IMP by the Investigator. Doses within an assigned cohort may only be changed at the discretion of the SRC. (As of Amendment 3, the SRC will be disbanded.)

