#### **8.1.2.2 Dose-delay Criteria**

IMP administration should be delayed for the following:

- Any Grade 2 or 3 IMP-related AE, with the following exceptions:
  - Grade 2 IMP-related fatigue or laboratory abnormalities do not require a treatment delay.
- Any Grade 3 IMP-related laboratory abnormality, with the following exceptions for lymphopenia or leukopenia, AST, ALT or total bilirubin or asymptomatic amylase or lipase:

- Lymphopenia or leukopenia of any grade does not require dose delay.
- If a subject has a baseline AST, ALT or total bilirubin that is within normal limits, delay dosing for drug-related Grade  $\geq 2$  toxicity.
- If a subject has baseline AST, ALT or total bilirubin within the Grade 1 toxicity range, delay dosing for IMP-related Grade  $\geq 3$  toxicity.
- If a subject has baseline AST, ALT, or total bilirubin within the Grade 2 toxicity range, delay dosing for IMP-related toxicity that increase by 2-fold or values  $> 8 \times \text{ULN}$ .
- Any Grade  $\geq 3$  IMP-related amylase or lipase abnormality that is not associated with symptoms or clinical manifestations of pancreatitis does not require dose delay. The Medical Monitor should be consulted for such Grade  $\geq 3$  amylase or lipase abnormalities. (As of Amendment 3, decisions regarding subject treatment should be made according to site standard of care as determined by the Principal Investigator.)
- Any AE, laboratory abnormality, or intercurrent illness which, in the judgment of the Investigator, warrants delaying the dose of study medication.

Subjects who require delay of IMP should be re-evaluated weekly or more frequently if clinically indicated and resume IMP dosing when re-dosing criteria are met.

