## **10 EFFICACY, PHARMACOKINETIC, SAFETY, AND OTHER VARIABLES**

### **10.1 Study Endpoints**

#### **Primary Endpoints:**

- Safety and tolerability will be evaluated by assessing AEs, and changes in physical examination findings, vital sign measurements, 12-lead ECG readings, and clinical laboratory evaluations.

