## **12.2 Populations to be Analyzed**

The following analysis sets will be used in the study:

- **Safety Analysis Set:** Includes all subjects who receive at least one dose of the investigational product (even a partial dose of either agent).
- **Efficacy Analysis Set:** Includes all subjects who receive combination therapy in Cycle 1 Day 1.
- **Pharmacokinetic Analysis Set:** Includes all subjects who provide at least one post-dose concentration measurement.
- **Pharmacodynamic Analysis Set:** Includes all subjects who provide at least one post-dose sample.

Evaluation of the data for this study will consist primarily of data listings and summary displays. Demographic and other baseline characteristic information will be summarized for the Safety Analysis and Efficacy Analysis Sets. Adverse events will be tabulated by body system, severity, and relation to treatment. Similar presentations will be provided for SAEs, AEs leading to discontinuation of IMP, and AEs leading to death. The tabulation of laboratory parameters will indicate the normal range for each parameter. Each value will be classified as falling above, below, or within the normal range.

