The number and percentage of subjects with TEAEs will be summarized by SOC and PT for Cycle 1 and for all cycles. A TEAE for Cycle 1 is defined as any event new or worsening prior to the Cycle 2 start date. Mogamulizumab-related TEAEs, nivolumab-related TEAEs, any IMP-related TEAEs, \geq Grade 3 TEAEs, mogamulizumab-related \geq Grade 3 TEAEs, nivolumab-related \geq Grade 3 TEAEs, any IMP-related \geq Grade 3 TEAEs, TEAEs leading to discontinuation of any IMP, any IMP-related TEAEs leading to any IMP-discontinuation, TEAEs leading to discontinuation of mogamulizumab, mogamulizumab-related TEAEs leading to discontinuation of mogamulizumab, TEAEs leading to discontinuation of nivolumab, nivolumab-related TEAEs leading to discontinuation of nivolumab, treatment-emergent SAEs, mogamulizumab-related treatment-emergent SAEs, nivolumab-related treatment-emergent SAEs, any IMP-related treatment-emergent SAEs, and fatal TEAEs will be summarized in the same manner. For these summaries, subjects with multiple AEs will be counted only once per SOC and PT.

In addition, summaries will be provided for the number and percentage of subjects with TEAEs, mogamulizumab-related TEAEs, nivolumab-related TEAEs, any IMP-related TEAEs by SOC and preferred term and by the highest NCI CTCAE grade. For these summaries, subjects with multiple adverse events will be counted only once by the highest NCI CTCAE grade within an SOC and preferred term.

As with any antibody, allergic reactions to dose administration are possible. Therefore, infusion-related acute reactions will be identified and summarized.

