Subject (Age/Gender)	Cancer Type	VT: Verbatim Term PT: MedDRA Preferred Term SOC: System Organ Class	Start Date	Stop Date	Start	Time	CTCAE Grade	Serious	Relationship Mogamulizumab/ Nivolumab	Action Taken Mogamulizumab/ Nivolumab/Treated?	Outcome/ DLT?
			Time/Day [1]	Time/Day	Cycle/ Cycle						
xxx-xxx (xx/F)	Lung	VT: xxxxxxxxxxxxxxxxxxxx*	YYYY-MM- DD/xx	xx/xx	DMI	x	No	NR/ NR	NN/ NR/No	REC/ No	
		PT: xxxxxx SOC: xxxxxx	YYYY-MM- DD/xx								
		VT: xxxxxxxxxxxxxxxxxxxx	YYYY-MM- DD/xx	xx/xx	PTM	x	No	R/ NR	DR/ NN/Yes	NREC/ Yes	
		PT: xxxxxx SOC: xxxxxx	YYYY-MM- DD/xx								

Continue with Expansion phase (Mogamulizumab x mg/kg + Nivolumab 240 mg).

[1] Day = Start/Stop date of adverse event - First dose date of the study drug (+1 if Start/Stop Date ≥ First dose date of the study drug); Cycle Day = Start date of adverse event - closest prior cycle Day 1 + 1.
 [2] Duration = Stop date of adverse event - Start date of adverse event + 1.
 Time point: NOI = N/A; PNI = Pre-Nivolumab Infusion; DNI = During Nivolumab Infusion; PTN = Post Nivolumab Infusion; PMI = Pre-Mogamulizumab Infusion; DMI = During Mogamulizumab Infusion; PTM = Post Mogamulizumab Infusion; UNK = Unknown.
 CTCAE Grade: 1 = Grade 1 (Mild); 2 = Grade 2 (Moderate); 3 = Grade 3 (Severe or Disabling); 4 = Grade 4 (Life-threatening); 5 = Grade 5 (Death).
 Relationship: NR = Not Related; R = Related.
 Action Taken: NN = None; DW = Drug Withdrawn; DR = Decrease Infusion Rate; DI = Dose Interrupted/Delayed; PA = Prior to Administration of SD/IP.
 Outcome: REC = Recovered/Resolved; NREC = Not Recovered/Not Resolved; RECS = Recovered/Resolved with Sequelae; RRC = Recovering/Resolving; FAT = Fatal; UNK = Unknown.
 * Non-treatment emergent event;
 Note: MedDRA Version 18.1 was used for coding.

The following listings will have similar layout as Listing 16.2.7.1:

Listing 16.2.7.2
Mogamulizumab or Nivolumab-related Adverse Events

Listing 16.2.7.3
Grade ≥ 3 Adverse Events

Listing 16.2.7.4
Serious Adverse Events (SAEs)

Listing 16.2.7.5
Adverse Events Leading to Discontinuation of Mogamulizumab or Nivolumab

Listing 16.2.7.6
Fatal Adverse Events

Listing 16.2.7.7
Infusion Reaction Adverse Events

Listing 16.2.8.1
 Laboratory Assessment - Chemistry

Treatment = Phase 1: Dose finding phase (Mogamulizumab 1 mg/kg + Nivolumab 240 mg)

Subject	Cancer Type	Lab Test (Unit)	Normal Range Low-High	Cycle	Sample Date (Days [1])	Lab Value	Flag	CTCAE Grade

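### The SAP tabulates adverse events that led to discontinuation, but none that led to dose delay or infusion interruption, the other two dosing actions the protocol names for toxicity

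*SAP*

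**What the plan says.** Protocol 10.1 makes safety and tolerability the primary endpoint: "Safety and tolerability will be evaluated by assessing AEs, and changes in physical examination findings", together with vital signs, ECGs and laboratory tests.

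Protocol 8.1.2 sets out how tolerability acts on dosing: "Doses of IMPs may be interrupted, delayed, or discontinued depending on how well the subject tolerates the treatment". Section 8.1.2.1 adds: "There will be no intra-patient dose reduction of either IMP by the Investigator". It leaves changes to a cohort's dose to the Safety Review Committee (SRC), which is disbanded as of Amendment 3. Section 8.1.2.2 opens with "IMP administration should be delayed for the following" and lists related Grade 2 or 3 events first, with exceptions. Under Section 7.5 both drugs stop together: "subjects will not be allowed to continue one investigational agent if the other is discontinued".

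For analysis, Protocol 12.2 says: "Similar presentations will be provided for SAEs, AEs leading to discontinuation of IMP, and AEs leading to death". SAP 4.13.1 follows it and lists "TEAEs leading to discontinuation of any IMP, any IMP-related TEAEs leading to any IMP-discontinuation, TEAEs leading to discontinuation of mogamulizumab", plus the remaining related and nivolumab variants. The shell of overview Table 14.3.1.1 has discontinuation rows and no row for delay or interruption.

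The data on the other two actions are collected. The legend of Listing 16.2.7.1 gives action taken for each drug, with the code "DI = Dose Interrupted/Delayed". Listings 16.2.5.1 and 16.2.5.2 carry infusion delay and infusion interruption as separate items, each with a reason.

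**The concern.** Delay is the usual first response to a related Grade 2 or 3 event in this protocol. Permanent discontinuation under Section 8.1.4 is tied mainly to events meeting the dose-limiting toxicity criteria, severe infusion or hypersensitivity reactions, and toxicity delays beyond 6 weeks. Even those long delays are allowed when the cause is a prolonged steroid taper. Table 8.2.2-1 recommends temporarily interrupting the infusion for Grade 1 or 2 infusion reactions.

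A subject whose dosing is held for toxicity and then resumed therefore appears in no table organised by dosing action. At stake is a plain tolerability question that the study report should answer from a table: in how many subjects did toxicity delay or interrupt the regimen, and which events were responsible?

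**Working it through.** **1. Count of planned outputs.** The SAP's list of tables runs from 14.3.1.1 to 14.3.1.14. With sub-numbers, in order:

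1 (.1) + 1 (.2) + 3 (.3) + 1 (.4) + 3 (.5) + 1 (.6) + 3 (.7) + 1 (.8) + 3 (.9) + 3 (.10) + 3 (.11) + 1 (.12) + 3 (.13) + 1 (.14) = 28.

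Discontinuation: 14.3.1.10.1-3 and 14.3.1.11.1-3, so 6. Delay or interruption: 0.

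**2. Does mogamulizumab relative dose intensity (RDI) fill the gap?** SAP 4.8 defines it as

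[(doses in Cycle 1 + 2 × later doses) / (4 × cycles)] × [28 × cycles / (last dose date + n* − first dose date)] × 100, with n* = 14 beyond one cycle.

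For C completed cycles (C ≥ 2) on schedule, the first bracket is (4 + 4(C − 1))/(4C) = 1. The span from first to last dose is 28C − 14 days, so RDI is 28C/28C = 100%. One 14-day delay adds 14 days to the span, so RDI = 28C/(28C + 14) = 2C/(2C + 1).

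| Cycles | RDI after one 14-day delay | Category in Table 14.1.3.1.x |
|---|---|---|
| 2 | 4/5 = 80.0% | 70 to <90% |
| 3 | 6/7 = 85.7% | 70 to <90% |
| 4 | 8/9 = 88.9% | 70 to <90% |
| 5 | 10/11 = 90.9% | 90 to <110% |
| 6 | 12/13 = 92.3% | 90 to <110% |
| 12 | 24/25 = 96.0% | 90 to <110% |

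A single delay is visible early, but from five cycles on it sits in the same category as perfect dosing. Repeated delays remain visible: two over 6 cycles give 168/196 = 85.7%, and three over 12 give 336/378 = 88.9%. RDI does not separate toxicity from other causes.

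**3. Does nivolumab RDI fill it?** SAP 4.8 takes the assigned dose as (last − first dose date) × 240/14, without adding the final dosing interval. For k doses:

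- On schedule, the span is 14(k − 1) and RDI = k/(k − 1): 200% for 2 doses, 150% for 3, 109.1% for 12. For one dose it is undefined, because the denominator is zero.
- With one 14-day delay and k ≥ 2, the span is 14k and RDI = k × 240/(k × 240) = 100% exactly.
- Skipping one intermediate dose gives the same span for the k doses received, so again 100%.

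A delayed subject thus looks fully dosed, and the nivolumab shell has no category rows.

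**4. Other exposure rows.** A delayed dose that is given later stays in the infusion count and in the count for its cycle and day. An infusion interrupted and then completed changes neither RDI nor those counts. It may lengthen infusion time (Tables 14.1.3.3.x and 14.1.3.4.x), but no cause is shown there.

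**5. Illustration of size.** The documents give no delay or discontinuation rate, so these rates are assumptions only. Take the Phase 2 ceiling of 184 subjects, 10% discontinuing for an adverse event, and 40% (range 20 to 60%) with at least one toxicity-related delay or interruption. Suppose every discontinuer also had a delay.

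- Discontinued: 184 × 0.10 ≈ 18.
- Delayed or interrupted: 184 × 0.40 ≈ 74 (184 × 0.20 ≈ 37; 184 × 0.60 ≈ 110).
- In no action-based table: 74 − 18 = 56 (37 − 18 = 19; 110 − 18 = 92).

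**The case against.** The strongest reply is that tolerability is well covered already. Adverse events are tabulated overall and by grade, relatedness, seriousness and fatal outcome. Infusion reactions, laboratory shifts, vital signs and QTc also have tables. The related events that trigger delays are in Tables 14.3.1.5.1-3 by highest grade. All of this stands. A reader might infer that most of the tolerability result stays in listings, and the documents do not support that. What is untabulated is the link from an event to a delay or interruption.

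Second, a reader might infer that a combination forcing repeated missed doses would look well tolerated in the tables. That is not supported either: repeated delays lower mogamulizumab RDI, and omitted doses lower its numerator and the counts by cycle and day. What remains is that these measures are all-cause and that the nivolumab formula conceals one 14-day delay.

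Third, the SAP does not depart from the protocol. Protocol 12.2 also names only discontinuation, and SAP Section 1 allows supplementary analyses. This is correct: the omission is in both documents, and no data are lost.

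Fourth, dose reduction is not ruled out altogether. The restriction binds the Investigator, and the SRC could change a cohort's dose. This also stands, but it does not alter how toxicity is handled in an individual subject.

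Finally, because both drugs must stop together, Tables 14.3.1.10.1-3 should largely coincide, and one might wish to drop one of them. Action taken is recorded for each drug, so the separate tables would show any departure from Section 7.5. They should stay.

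**Conclusion.** The point holds as a limited reporting gap in the analysis of the primary endpoint. Two of the three dosing actions that the protocol names for toxicity have no adverse-event table (0 of 28, against 6 for discontinuation). The indirect measures cannot replace one: they are all-cause, one 14-day delay leaves mogamulizumab RDI in the top-compliance range from five cycles on, and nivolumab RDI returns exactly 100%.

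The table count and the RDI results rest only on the documents. The RDI figures assume that a delay shifts all later doses and that everything else is on schedule. The figures of 18, 74 and 56 subjects are illustrative. The 10% rate is not varied, 184 is a maximum, and the events of those 56 subjects would still appear in the incidence and grade tables. The finding does not depend on them. Sample size and error rates are unaffected.

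**What to change.** 1. In SAP 4.13.1 and Table 14.3.1.1, add rows for treatment-emergent events leading to dose interruption or delay: any, any-IMP-related, mogamulizumab-related and nivolumab-related.
2. Add one table of these events by system organ class and preferred term, in the layout of Table 14.3.1.2, derived from action code DI. State how an event is counted if it first delayed dosing and later led to withdrawal.
3. In Tables 14.1.3.1.x and 14.1.3.2.x, add the number of subjects with at least one delayed infusion and, separately, at least one interrupted infusion, by reason. Take these from the dosing records behind Listings 16.2.5.1 and 16.2.5.2. Code DI merges the two actions and cannot tell a brief pause from a postponed dose.
4. Keep Tables 14.3.1.10.1-3.

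The cost is one extra table and a few rows from fields already collected. If the SAP is not reopened, the same outputs can be produced as supplementary analyses and identified as such in the study report, as SAP Section 1 allows.
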